**Table 3: Parameters Estimates of Preliminary Updated Population PK Model**

Updated model 6 transit-cmt (data LAF-A,-B,-C)		
Parameter (Units)	Estimate (RSE,%)	IIV (%)
CL/F (L/h)	37.6 (4.81)	28.6
V c /F (L)	399 (5.54)	22.4
Q/F (L/h)	48.6 (6.46)	-
V p /F (L)	847 (6.16)	-
KA (/h)	5.36 (3.25)	23.6
F	1 FIX	26.3
RUV (CV%)	0.161 (10.5)	40.1

IIV = inter-individual variability (%); RSE = residual standard error; CV = coefficient of variation; CL/F = apparent clearance; Vc/F = apparent central volume of distribution; Q/F = apparent intercompartmental clearance; Vp/F = apparent peripheral volumes of distribution; KA = absorption rate constant; RUV = residual unexplained variability.

## 4.2. Analysis Overview

The analysis will consist of the following steps:

1. **Exploratory Analysis:** A graphical analysis will be initially performed to explore baseline covariates and their correlations, JNJ-67953964 plasma concentration data, and change from baseline MADRS and SHAPS total score data collected in Study 67953964MDD2001 stratified by lead-in placebo response;
2. **External Evaluation of the Population PK Model:** An external evaluation of the preliminary updated population PK model will be performed to assess the predictive performance of this population PK model for the patient population in 67953964MDD2001. GOF plots, VPC's, and pcVPC's will be used as external evaluation methods. Refinements of the preliminary population PK model structure may be performed in case the external evaluation is unsuccessful and therefore modifications to the model are required to adequately describe the both the Phase 1 and the current 67953964MDD2001 data;
3. **Determination of Individual Population PK Parameter Estimates:** The individual population PK parameter estimates will be obtained from the population PK model obtained from the previous steps. A graphical covariate analysis will be performed to explore potential parameter-covariate relationships. Covariates that become significant and clinically relevant will be incorporated into the model.;
4. **Derivation of Individual Exposure Parameters:** Using the individual population PK parameter estimates, the individual estimates of the area under the plasma concentration time profile of JNJ-67953964 over 24 hours ( $AUC_{0-24h}$ ), maximum JNJ-67953964 plasma concentration ( $C_{max}$ ) and the pre-dose JNJ-67953964 plasma concentration ( $C_{0h}$ ) will be derived for each visit in all subjects from Study 67953964MDD2001;
5. **Exploration of Relationship between Exposure and MADRS and SHAPS:** Exploratory analyses will be performed to graphically inspect the response variables. During the analyses, at minimum, the following graphs will be explored: individual  $AUC_{0-24h}$  versus MADRS and SHAPS total score, both absolute and change from baseline. Correlation between MADRS and SHAPS total scores. Exploratory plots will be stratified by lead-in placebo-response and by visit. The exposure-response analysis (step 6 and 7) will be performed for the efficacy endpoints if the exploratory analysis shows a relationship in exposure-efficacy;
6. **MADRS and SHAPS PK/PD Modelling:** The change from baseline MADRS and SHAPS total score will be modelled separately using specific parameters for placebo effect, and drug effect, using individual JNJ-67953964 exposure estimates in the drug effect sub-model. Baseline scores, co-medication, gender, race and age at baseline will be tested as potential covariates. Primary analysis on MADRS will be performed on the enriched population (lead-in non-responders). In case no effect on MADRS is found, change from baseline SHAPS total scores will be analyzed on the full dataset. If appropriate, the analysis on MADRS may be repeated on the full dataset, where both lead-in placebo response as well as baseline SHAPS total score will be tested as covariate in the model;
7. **Simulations of change in MADRS and SHAPS:** Based on the final PK/PD model (including covariates, if any), model based simulations of the drug effect on MADRS and SHAPS change from baseline (i.e. net MADRS/SHAPS change from baseline after correction for placebo response) will be generated;

8. **Exploration of Exposure versus Safety Parameters:** Exploratory bar plots of AE grade versus exposure quantiles will be generated for the AE's of interest: pruritis and GI complaints. Other AE's with one or more observations of grade 3 or higher may be included in the exploratory analysis as well. If appropriate, a logistic regression may be used to describe the relationship between exposure and the occurrence of an AE.
9. **Reporting:** Prepare the report in accordance with the FDA and EU guidance on population PK.

#### 4.3. Exploratory Analysis

The aim of the exploratory data analysis will be twofold: (i) graphical presentation of the data in order to define the range of concentrations, guide the structural model considerations, and facilitate outlier identification; (ii) examination of covariate correlations which may help in building a covariate sub-model and avoid confounding bias.

Individual, and mean or median, plasma concentration – time profiles will be plotted on linear-linear and logarithmic-linear scales after stratification by lead-in placebo response, SSRI or SNRI co-medication and other appropriate covariates. Data points will be considered as potential outliers if they substantially deviate from adjacent points in the concentration-time profiles and may be omitted from the model building (Section 4.4.2).

In addition, the exploratory graphical analysis of every quantitative covariate will consist of a histogram, box plots and plots of quartiles of covariate distributions and quantiles of standard normal distribution (QQ plot). Summary statistics of each quantitative covariate by study will be provided. Moreover, correlations between quantitative covariates and boxplots for every quantitative covariate against every categorical covariate will be explored.

#### 4.4. Population PK Model Development

##### 4.4.1. External Evaluation of the Preliminary Updated Population PK Model

An external model evaluation will be performed to assess the predictive performance of the preliminary updated population PK model for the current analysis dataset. For this purpose, the following diagnostics will be used:

- Visual Predictive Check (VPC) and Prediction Corrected Visual Predictive Check (pcVPC). The VPC will be performed to provide visual comparison between distributions of simulated data using the previously developed model with the analysis dataset. The pcVPCs differs from traditional VPC in that the dependent variable has been subjected to a prediction correction before the statistics are calculated. Prediction correction aims to correct for the differences within a bin coming from different independent variables in the model and hence, clearly diagnose model misspecifications in both fixed and random effects. In the VPC, the 5th, 50th, and 95th percentiles of the observed data will be compared with the model-based predicted percentiles for each bin across time and replicates. A total of 1,000 replicates of the analysis dataset will be generated from the preliminary population PK model. Uncertainty in parameters estimates will not be considered in this analysis.

- Goodness-of-fit (GoF) plots: A maximum a posteriori (MAP) estimation using the preliminary population model as prior information will be used to estimate the individual population PK model parameters for subjects included in Study 67953964MDD2001. This analysis will be conducted using the MAXEVAL=0 option in NONMEM. The following goodness-of-fit plots will be generated in order to assess the deviation of population and individual predictions from the observed data:
  - Observations vs population predictions (PRED);
  - Conditional weighted residuals vs PRED and vs time since last dose;
  - Observations vs individual predictions (IPRED);
  - Individual weighted residuals vs IPRED and vs time since last dose;
- Numerical Predictive Check (NPC). The NPC will be performed on the mean and the standard deviation (SD) of the exposure metrics ( $AUC_{24h}$  and  $C_{0h}$ ), since these reflect the central tendency and the variability of the exposure metrics. Within each replicate, the mean and SD of the exposure metrics to be used in the ER analysis will be computed. The model-based distribution of the mean and SD of the exposure metrics across replicates will be obtained and its 2.5th and 97.5th percentile will be used to calculate the lower and upper limit of the 95% confidence interval (CI) of the model-based predicted mean and SD of the exposure metrics, which will be then compared to the actual metric of exposure obtained from the Study 67953964MDD2001. Based on the parameter estimates of the previously developed model, 1000 replicates of the analysis dataset will be simulated.

Adequacy of the model will be assessed by the ability of the model to capture the central tendency and the variability of the data (as attested by the VPC/pcVPC plots) and to provide population and individual predictions without significant bias (confirmed by the GoF plots).

If the external evaluation is unsuccessful, potential refinements of the preliminary population PK model (e.g. modifications of the model structure, re-estimation of population parameters, addition of study-specific factors, etc) will be evaluated in order to adequately describe the data from Study 67953964MDD2001 and the three Phase 1 studies, LAF-A, LAF-B and LAF-C. If a model update is performed, the criteria described in Section 4.9 may be used to compare different candidate models.

#### 4.4.2. Identification of Outliers

An outlier is defined as an aberrant observation that significantly deviates from the rest of the observations in a particular subject or as a subject when all observations for that subject are aberrant. Outliers may be excluded from the analysis as they are known to have negative impact on the convergence and/or introduce bias in parameter estimates. The outlier detection in the full PK profiles will be based primarily on visual examination of individual and pooled concentration-time profiles. Data points will be considered as potential outliers if they substantially deviate from adjacent points in the concentration-time profiles and if their conditional weighted residual is large,

eg, greater than +/- 6 units. Only the observations that meet both criteria will be identified as outliers. The observations will be excluded from the analysis by flagging them with "C" in the NONMEM dataset. In a subsequent step, it may be investigated if the outliers influence the population and individual population PK model parameter estimates.

#### 4.4.3. Covariate Analysis

The model described above (i.e. previously developed preliminary PK model or updated PK model) may constitute the base model for covariate model development. The basis of the covariate model should be the clinical significance of the covariate effects rather than their statistical significance. The model building will consist of a number of steps based on the guidance by various regulatory authorities;

1. A list of covariate/parameter pairs that are physiologically plausible are selected from exploratory plots of EBE vs covariates and based on generalized additive models (GAM) on the regression between each EBE and the covariates. Only covariates that are statistically significant ( $p < 0.001$ ) with model parameters will be considered as potentially clinically relevant and will be further evaluated. Covariates will include gender, race, age, body weight, albumin and creatine clearance at baseline. If a candidate covariate can be represented as either a categorical or continuous covariate, the continuous covariate is usually preferred.
2. Trim the list using the following criteria:
  - a. When two or more covariates have correlation greater than 0.3 the most physiologically plausible should be retained and the others discarded because retaining them gives rise to the co-linearity problem.
  - b. Remove covariates having insufficient sample sizes, ie, represented by less than 20 subjects per parameter.
  - c. Overall number of subjects vs. number of covariate evaluations (number of covariate parameters)  $\geq 10$ .
3. Fit the full model. If the full model does not converge, then the forward stepwise selection method can be taken based on a p-value  $< 0.01$ .
4. The full covariate model from step 3 may be reduced based on the point estimates of the magnitude of the effect of the covariate on the PK parameter using a clinically meaningful threshold (if available), to obtain the final covariate model. If deemed necessary, this step may be preceded by backward elimination using a more stringent nominal p-value of 0.001.
5. A diagnostic plot should be made. It is useful to generate a forest plot or equivalent for the final covariate model to assist identification of clinically relevant covariates. Statistical tests on empirical Bayes' estimates (EBE's) are preferred over exploratory plots of EBE's versus the covariates if the shrinkage is large (eg,  $>35\%$ ).

A discussion of the physiological plausibility and clinical relevance of the final covariate model may be included in the discussion section of the report. We must take into consideration that the model is based on an association between the PK parameters and the covariates which can only be interpreted as causative if there are good scientific reasons for doing so.

#### 4.4.4. Refining the Covariance Structure

Correlation between PK parameters may be tested after all significant fixed covariate effects have been included in the model. The individual ETAs will be examined graphically by plotting each ETA against all others. If visual inspection of plots reveals any correlation, the corresponding block may be introduced into the OMEGA matrix to test its significance using the likelihood ratio test. If implementing a correlation significantly improves the fit, the block will be kept in the model. The process will be repeated until no further improvement of the fit can be achieved. A model with a full block of correlations between random effects will be used as a reference to determine the maximum possible improvement by optimizing covariance structure.

#### 4.5. Determination of Individual Population PK Parameter Estimates

The individual population PK parameter estimates of  $AUC_{0-24h}$ ,  $C_{max}$  and the pre-dose JNJ-67953964 plasma concentration ( $C_{0h}$ ) will be calculated for each subject at each visit either by fixing the population parameters of the full covariate population PK model.

Correlation between population PK parameters will be assessed.

#### 4.6. MADRS and SHAPS PK/PD Modelling

Exploratory plots of individual  $AUC_{0-24h}$  versus MADRS and SHAPS total score, both absolute and change from baseline, stratified by lead-in placebo-response and by visit will be created. The exposure-response analysis will only be performed for the efficacy endpoints if the exploratory analysis shows a relationship in exposure-efficacy.

The MADRS and SHAPS total score data will be modelled using specific parameters for baseline response, placebo effect, and drug effect, according to the following general equation:

$$y_{ij} = (\theta_1 v_1 + \theta_2 v_2 + \theta_3 v_3 + \theta_4 v_4 + \theta_5 v_5 + \alpha_i) + f_i(v_j, C_i) + \varepsilon_{ij}$$

where  $y_{ij}$  represents the change from baseline MADRS or SHAPS total score for the  $i$ -th subject at the  $j$ -th time point ( $j=1..5$  for the 5 post-baseline visits in Week 1, 3, 4, 5 and 6),  $\theta_{1-5}$  represent the fixed effects for the placebo response at the post-baseline visits, i.e.  $j=1..5$  (with  $v_{1-5}$  denoting indicator variables with value 1 when  $j$  is equal to Treatment Week 1, 3, 4, 5 and 6),  $\alpha_i$  represents the random effect parameter for non-drug-related response,  $f_i(v_j, C_i)$  representing the concentration-effect relationship for JNJ-67953964 in the  $i$ -th subject at the post-baseline visits, i.e.  $j=1..5$  as a function of the exposure metric  $C_i$ , and  $\varepsilon_{ij}$  represents the residual variability associated to measurement  $y_{ij}$ . Baseline is defined as treatment baseline, i.e. last observation before the first dose.

The inter-individual variability (IIV) random effect  $\alpha_i$ , and any random effect within  $f_i$  will be assumed to be normally-distributed, zero-mean, uncorrelated random variables. The residual variability random effects  $\varepsilon_{ij}$  will be assumed to be normally-distributed, zero mean, uncorrelated random variables that are also uncorrelated with respect to  $\alpha_i$ , and any random effect within  $f_i$ . Alternative distributions for the IIV and the residual variability random effects may be considered if needed. If warranted by the data, parametric functions of time (e.g. linear, exponential) may be used to describe the placebo effect.

The exposure metrics to be used in the PK/PD model will be  $AUC_{24h}$  (see Section 4.5). Additional exposure metrics may be tested if the  $R^2$  of the correlation between PK parameters is less than 0.8.

In case of  $C_{0h}$ , observed pre-dose exposure may be used as an alternative to the model-estimated  $C_{0h}$ .

The drug effect sub-model may be parametrized as a linear, or if the exposure range allows,  $E_{max}$ , sigmoid  $E_{max}$ , or exponential function, as determined by model building criteria (Section 4.9). In case a delay in onset of drug effect will be observed during the exploratory analysis, the delay will be fit using an appropriate delay function, such as a sigmoid. Additional functional forms of the drug effect sub-models may be tested. Baseline MADRS or SHAPS will be tested as covariate on both drug-related and drug-non-related response in order to assess the potential influence of higher/lower baseline disease severity on MADRS and SHAPS change. Gender, race, and age at baseline will also be tested. Lead-in placebo response will be tested as covariate on models based on the full dataset for change from baseline MADRS scores. Lead-in placebo response will not be tested as covariate for change from baseline SHAPS models, as no effect was observed on SHAPS during the lead-in period based on blinded data. Additional parameter-covariate relationships may be tested if required.

Primary analysis on MADRS will be performed on the enriched population (lead-in non-responders). In case no effect on MADRS is found, change from baseline SHAPS total scores will be analyzed on the full dataset. If appropriate, the analysis on MADRS may be repeated on the full dataset, where both lead-in placebo response as well as baseline SHAPS total score will be tested as covariate in the model.

Change from baseline MADRS or SHAPS total scores obtained during the withdrawal period (Day 78) may be explored and included in the model as function of exposure if deemed appropriate.

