9.2. Efficacy Analyses

9.2.1. Primary

Primary efficacy analyses will be based on the intention-to-treat analysis set from enriched population (eITT) which consists of randomized lead-in placebo non-responders receiving at least one dose of study medication and having at least one post-treatment baseline efficacy measurement.

The JNJ-67953964 treatment group will be compared with placebo using the primary efficacy endpoint: change from treatment baseline in MADRS score during the treatment period. The comparison will be performed by means of a mixed-effects model for repeated measures

(MMRM), with time, treatment (placebo, JNJ-67953964) and time-by-treatment interaction as factors and baseline total MADRS score as a continuous covariate. Other covariates of interest may be included in the MMRM model. The treatment-placebo differences will be obtained using the appropriate contrast in the MMRM models at the 6-week endpoint.

Sensitivity analyses of the primary endpoint will be performed using an analysis of covariance (ANCOVA) model; these will be detailed further in the Statistical Analysis Plan.

In addition, same MMRM model will be fitted on full intention-to-treat analysis (fITT) set consisting of all the randomized subjects receiving at least one dose of study medication and having at least one post-treatment baseline efficacy measurement.

Missing data mechanisms exploration and possible imputation methods for primary efficacy variable will be described in detail in Statistical Analysis Plan.

Descriptive statistics for actual values and changes from baseline for MADRS Score at each time point of the double-blind treatment phase will be provided by treatment group using both: eITT and fITT analysis sets. Mean differences between the treatments with corresponding confidence intervals (CIs) will be reported.

Frequency tables for response and remission of depressive symptoms (derived from the MADRS) will be provided by treatment group at each time point of the double-blind treatment phase using both: eITT and fITT analysis sets. Chi square test to test the overall differences between the treatment groups will be performed.

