## 2. OBJECTIVES

The primary objectives of the population pharmacokinetic (PK) and pharmacodynamic (PD) analysis are as follows:

- To characterize the pharmacokinetics of 10 mg qd JNJ-67953964 after oral administration, including
  - an exploratory analysis to determine if any relevant covariate could explain the variability in exposure of JNJ-67953964;
  - derivation of individual exposure parameters for JNJ-67953964 (i.e. area under the plasma concentration-time profile of JNJ-67953964 over 24 hours, AUC0-24h maximum plasma concentration, Cmax, and pre-dose plasma concentrations, C0h). Exposure metrics will be derived from the popPK model on the study days with MADRS and SHAPS assessments;
- To explore the relationship of JNJ-67953964 exposure with efficacy using the change from baseline in Montgomery-Asberg Depression Scale (MADRS) total score and change from baseline in Snaith-Hamilton Pleasure Scale (SHAPS);
- To explore potential relationship between JNJ-67953964 exposure and pre-defined safety parameters. AEs of special interest may include pruritus and gastrointestinal (GI) complaints.

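### The exposure-response model is fitted only if plots of the same data show a relationship, with no criterion: a flat look leaves no slope or interval, and a passed gate tends to overstate a real PK/PD effect

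*SAP*

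**What the plan says.** SAP 2 lists, among the primary objectives of the PK/PD analysis, "To explore the relationship of JNJ-67953964 exposure with efficacy using the change from baseline" in MADRS and SHAPS. Protocol 3 has the same aim as part of a secondary objective.

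SAP 4.2 step 5 and SAP 4.6 begin with plots of individual AUC against MADRS and SHAPS, "both absolute and change from baseline, stratified by lead-in placebo-response and by visit will be created". Step 5 continues: "The exposure-response analysis (step 6 and 7) will be performed for the efficacy endpoints if the exploratory analysis shows a relationship in exposure-efficacy". SAP 4.6 is firmer: "The exposure-response analysis will only be performed for the efficacy endpoints if the exploratory analysis shows a relationship in exposure-efficacy". Neither section says what counts as a relationship, in which panel or direction, or who decides.

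The base model is already written in SAP 4.6: a fixed placebo response for each of the five post-baseline visits, a subject random effect, and a drug effect as a function of exposure, possibly linear. SAP 4.7 uses the final model for the Week 6 simulations, including the probability of a drug effect of at least 1, 2 or 3 points. A point estimate with 90% CI is produced only in simulation (c). Simulations (a), (b) and (d) leave out parameter uncertainty.

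On SHAPS, step 6 of SAP 4.2 says "The change from baseline MADRS and SHAPS total score will be modelled separately using specific parameters for placebo effect, and drug effect". The same step and SAP 4.6 add: "In case no effect on MADRS is found, change from baseline SHAPS total scores will be analyzed on the full dataset". The SAP does not define the absence of a MADRS effect.

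**The concern.** Whether a model is fitted depends on how its own data look. This has two consequences.

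- **Gate failed.** The result is a set of plots without an estimate. Nobody can say whether the data exclude a useful slope or are too noisy to show one. With a single planned dose, exposure among treated subjects varies only through between-subject differences, so noise is a realistic explanation.
- **Gate passed.** Estimates that cleared a threshold are on average too large when the true effect is real but modest. The 90% CI and the simulated probabilities of a 1-, 2- or 3-point effect take no account of the selection.

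The SHAPS rule is a separate matter. Whether SHAPS is analysed on the full dataset depends on another outcome in the same subjects, through a condition that is not defined.

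**Working it through.** **1. The plan's own figure.** Protocol 9.1 gives effect size 0.45, SD 11, one-sided alpha 0.20 and power 90%. The planned difference is 0.45 × 11 = 4.95 points. n per arm = 2 × (0.8416 + 1.2816)² / 0.45² = 9.016 / 0.2025 = 44.5, so 45, as stated. Power at 45 per arm is 90.2%.

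**2. The gate as a cut-off.** The SAP gives no threshold, so a range is assumed: a one-sided look at 0.50, 0.20 or 0.05, with normal cut c = 0, 0.8416 or 1.645. For true effect θ and standard error SE, let a = c − θ/SE. Then

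- probability of passing = 1 − Φ(a)
- mean estimate among passes = θ + SE × φ(a) / (1 − Φ(a))

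**3. Placebo plotted at zero exposure.** Here SE is approximated by the two-arm value, 11 × √(2/45) = 2.32. Example with θ = 4.95 and a gate of 0.20: a = 0.8416 − 4.95/2.319 = −1.293; φ(a) = 0.1729; pass 0.902; mean = 4.95 + 2.319 × 0.1729/0.902 = 5.39.

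| True effect | Gate | Passes | Mean if passed | Ratio |
|---|---|---|---|---|
| 4.95 | 0.50 | 98.4% | 5.05 | 1.02 |
| 4.95 | 0.20 | 90.2% | 5.39 | 1.09 |
| 4.95 | 0.05 | 68.8% | 6.14 | 1.24 |
| 2.48 | 0.50 | 85.7% | 3.09 | 1.25 |
| 2.48 | 0.20 | 58.9% | 4.01 | 1.62 |
| 2.48 | 0.05 | 28.2% | 5.25 | 2.12 |

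**4. Active subjects only.** SAP Table 3 gives between-subject variability of 28.6% on CL/F and 26.3% on F. If these are independent, the CV of AUC is √(0.286² + 0.263²) = 0.389. With an effect proportional to AUC and 45 active subjects, the SE at mean exposure is 11 / (√45 × 0.389) = 4.22 points. At the planned 4.95 points:

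| Gate | Passes | Fails | Mean if passed | Ratio |
|---|---|---|---|---|
| 0.50 | 88.0% | 12.0% | 5.91 | 1.19 |
| 0.20 | 63.0% | 37.0% | 7.48 | 1.51 |
| 0.05 | 31.8% | 68.2% | 9.68 | 1.96 |

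Under these assumptions, a drug with the full planned effect would look flat at the 0.20 gate in about 37% of trials, and no slope or interval would be produced.

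**5. A gate open in both directions.** The SAP asks only for a relationship, not a favourable one. With b = −c − θ/SE, the mean among passes is θ + SE × [φ(a) − φ(b)] / [1 − Φ(a) + Φ(b)]. Using the step 3 SE and the 0.20 cut:

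- θ = 2.475: a = −0.226, b = −1.909; mean = 2.475 + 2.319 × (0.3889 − 0.0645)/0.617 = 3.69, ratio 1.49 instead of 1.62.
- θ = 4.95: the ratio stays at about 1.09.
- θ = 0: φ(a) = φ(b), so the mean is 0.

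**6. The SHAPS trigger.** It fires when the MADRS estimate is low. If the two estimates have correlation ρ and neither scale has a true effect, the mean SHAPS estimate given MADRS below the 0.20 cut is −ρ × φ(0.8416)/Φ(0.8416) = −ρ × 0.280/0.80 = −0.35ρ standard errors. That is −0.11 to −0.21 for assumed correlations of 0.3 to 0.6. Any shift is small and towards a smaller SHAPS effect.

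**The case against.** The strongest reply is that nothing decisive sits behind this gate. The PK/PD objective is exploratory, Protocol 9.4 promises this work only where feasible, the plots are made in every case, and the condition is disclosed in advance. The treatment effect is estimated regardless: Protocol 9.2.1 says "The treatment-placebo differences will be obtained using the appropriate contrast in the MMRM models at the 6-week endpoint", with the MADRS MMRM fitted on both the enriched and the full set. Protocol 9.2.2 does the same for SHAPS, and both sections report mean differences with CIs. This stands. A reader might infer that every reported drug effect is selected, or that a null result would go unquantified. The documents do not support either. What goes unquantified is the exposure-response slope, and an MMRM that compares arms does not supply it.

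The sizes can also be challenged. The cut-offs are assumed, and 2.32 is the SE of a two-arm contrast, not of an AUC slope. SAP 4.8 assigns placebo subjects zero exposure for the safety plots, but the SAP does not say whether they appear on the efficacy plots. With a loose gate and the planned effect, inflation is only 2%. All of this is fair, and it is why a range is shown. A reader might also infer that an inactive drug would show a spurious benefit on average. That needs a gate that passes only favourable patterns, which the text does not specify; a gate open both ways averages zero under no effect.

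Finally, the SHAPS sentence does not contain the word *only*, and SAP 4.2 step 6 and SAP 4.6 say both scales are modelled. A reader might infer that SHAPS is inflated in the same way as MADRS. The trigger is a MADRS null, so it is not.

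**Conclusion.** The point holds for the PK/PD analysis. The gate is explicit, uses the data it then models, and has no criterion. When it fails, a stated objective of this SAP ends without a slope or interval, and failure is weak evidence of flatness. When it passes, a real effect and the simulations built on it tend to be overestimated. With placebo at zero exposure and one-sided gates of 0.50 to 0.05, the inflation is about 2% to 24% at 4.95 points and about 25% to 112% at half that. If only active subjects are plotted, it is 19% to 96% at 4.95 points.

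These figures rest on four assumptions that are not in the documents: a visual check that behaves like a cut-off on the estimate, the cut-offs themselves, an effect proportional to AUC with independent variability in CL/F and F (active-only case), and SD 11 with 45 per arm carried over from the primary comparison. A gate open in both directions lowers the inflation at half the planned effect and barely changes it at the full effect for the 0.20 cut.

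The full-dataset SHAPS rule is outcome-dependent and undefined, and it sits awkwardly beside the statement that both scales are modelled. This is a clarity and selection problem, not a demonstrated upward bias. No randomized efficacy comparison is affected.

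**What to change.** In SAP 4.2 step 5 and SAP 4.6, remove the condition. Fit the base model of SAP 4.6, visit-specific placebo response plus a linear AUC term, whatever the plots show: MADRS in lead-in non-responders and SHAPS in the full dataset. Report the slope and its 90% CI each time. Use the plots only to choose the functional form (linear, Emax, delayed onset). Drop the MADRS-null trigger, so that the full-dataset SHAPS analysis no longer depends on the MADRS result. With the linear model always fitted and reported, this selection bias disappears for that estimate.

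The cost is a few extra model runs and a short SAP edit. The one drawback is that the report may contain an imprecise slope, but its interval will show that openly.
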